# **Statistical Analysis:**

### Demographic and baseline characteristics:

Demographic and baseline characteristics including gender, age, race, ethnicity, and co-morbidities will be summarized for each treatment group and overall. The demographic and baseline characteristics summary will be based on all randomized subjects.

Baseline values for efficacy parameters (ACT, quality of life score, PAMSE) will also be presented for each treatment group and overall based on all randomized subjects.

For continuous variables, non-missing will be used to calculate the mean, median, SD, IQR, minimum and maximum by treatment group and overall. For categorical variables, the count and percentages of each possible value will be tabulated by treatment group and overall.

All comparisons of baseline characteristics between treatment groups will be adjusted for potential household clustering using robust standard errors. For continuous variables, comparability of treatment groups will be assessed using general linear models. For discrete variables, comparability will be assessed using the Cochran-Mantel-Haenszel general association test. P-values will be displayed as descriptive statistics of comparability in order to identify potential baseline imbalances with an alpha level of 0.05.

# AIM 1. Determine factors influencing clinical and psychosocial outcomes.

Clinical and psychological outcomes of interest include the 12-month rate of asthma-related oral corticosteroid use, ED visits, and hospitalizations, as well as change in mean ACT scores (range of 0 to 27) from baseline to end line (12 months). Psychological outcomes of interest include quality of life score (range of 1 to 7), parental self-efficacy score, and the number of school days missed due to asthma. Potential predictors of outcomes include age (4 to 7 years vs. 8 to 17 years), gender (M vs. F), race/ethnicity (non-Hispanic white, non-Hispanic Black, Hispanic, vs. others), insurance status (private/public), and co-morbidities.

Each count variable (asthma-related oral corticosteroid use, ED visits, and hospitalizations) will be analyzed by mixed negative binomial regression analysis adjusting for treatment, all potential predictors, and including maximal random effect structures (i.e., slope and intercept as allowed by the model) of family and clinic. VIFs (variance inflation factors) will be computed for each predictor. Highly correlated predictors (i.e. predictors that can be well-explained by other predictors) will be dropped from the model to avoid multicollinearity issues. Model fit criteria, parameter estimates, and precision of parameter estimates will all be evaluated to select the most parsimonious model.

For each continuous primary outcome variable (i.e., ACT score), change-from-baseline score at each visit will be analyzed using mixed linear regression models, adjusting for treatment, time point, baseline score, all potential predictors, and including random effects (i.e., both slope and intercept) of family and clinic. A treatment by time interaction will be included to evaluate whether the effect of the treatment on the primary outcome varies by time point. VIFs will be investigated for each predictor, and those with high VIFs (VIF>=10) will be dropped from the model to avoid multicollinearity issues. An unstructured covariance (UN) matrix will be assumed. Model fit criteria, parameter estimates, and precision of parameter estimates will also be used to select the most parsimonious model. Model diagnostics will be performed to check model assumptions. All analyses will be performed using statistical analytic software Stata Version 15.1.

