This interface will include data on both ICS and SABA inhaler use. The interface will also have flags to notify the office of under or overuse of inhalers, with a protocol in place to reach out to patients. We will also be assessing the factors associated with the feasibility and sustainability of the Remote Health Management Platform by the healthcare team. This will be done by weekly contact with the healthcare team, rapid cycle improvement of the web portal, and written assessments. Follow-up assessments through interview will be conducted at the end of the trial with health providers.

[figure not shown]

Figure 1. Study Arms

Participant Sites

The participant sites will be pediatric clinics in the Chicagoland Area. Each site in this proposed study has a strong history of research collaborations with [name], which includes the ability to recruit and retain patients in research studies.

We will be recruiting from at least four of the following sites:

- Children’s Healthcare Associates
- Chicago Family Asthma and Allergy
- Clark/Deming Resident Clinic (Lurie Children’s)
- Pulmonary Clinic (Lurie Children’s)
- Lurie Children’s Uptown Clinic

Study Design and Procedures

1. **Design:** We will conduct a randomized controlled trial comparing asthma inhaler use and asthma-related outcomes between children who either receive the Remote Health Management Platform (intervention) or Standardized Education (control) for asthma management. We will use a prospective cohort design to determine the effect of the intervention on the aforementioned outcomes.

We will enroll patients from Chicago pediatric clinics, as well as inpatient units at Lurie Children’s Hospital. At enrollment, we will randomize children to either the Remote Health Management Platform (intervention) group or the Standardized Education group (control).

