| Parent-reported values (un-validated) | School days missed due to asthma | 5 times in total (baseline, 3 months, 6 months, 9 months, study completion) |
| Pediatric Caregiver Asthma-related Quality of Life Questionnaire (PACQLQ) | Parent form of how their child's asthma is affecting both their lives and the life of their child | 5 times in total (baseline, 3 months, 6 months, 9 months, study completion) |

Parental Management Outcomes

| Source | Outcome | Time Point |
|-----------------------------------|--|---|
| Parent report (Survey) | Feasibility and acceptability of Platform | 5 times in total (baseline, 3 months, 6 months, 9 months, study completion) |
| Remote Health Management Platform | Frequency of use of the application (synching) | Monthly data pull |

Physician and Clinical Team Outcomes

| Source | Outcome | Time Point |
|-----------------------------------|---|---|
| Remote Health Management Platform | ICS and SABA use | Monthly download |
| Web Portal/Epic | Asthma-related ED visits, hospitalizations, and oral corticosteroid prescriptions/courses | Monthly Epic data pull |
| Clinician Survey | Feasibility and acceptability of the Platform | 1 month into the study, 6 months and study completion |
| Physician Survey | Feasibility and acceptability of the Platform | 1 month and study completion |
| Remote Health Management Platform | Frequency of use of the web portal | Monthly data pull |

Data Analysis:

Primary Outcomes

- *ACT*: Parent-reported test on their child's asthma control
- *Asthma-related hospitalizations*: Data will be obtained from the EMR and parent report.
- *Asthma-related ED visits*: Data will be obtained from the EMR and parent report.
- *Asthma-related oral corticosteroid use*: Prescription/course data will be obtained from the EMR and parent report.

Secondary Outcomes

- *Inhaler Use*: Use data, including frequency of both SABA and ICS inhalers, will be obtained via the sensor throughout the study period.
- *PAMSE*: Parental Asthma Management Self-Efficacy; self-report survey that measures parental self-efficacy for the management and prevention of acute exacerbations of asthma.
- *PACQLQ*: Paediatric Asthma Caregiver's Quality of Life Questionnaire; will assess the impact of their child's asthma on their lives, the lives of their children with asthma, and the family as a whole.

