4. In the past week, how many alerts did you receive due to patients overusing albuterol?
 - One
 - Two

- 3 or more
- 5. In the past week, how many times did you have to follow-up with patients regarding their underuse of their controller medication?
 - Once
 - Twice
 - 3 or more times
- 6. In the past week, how many alerts did receive due to patients underusing their controller medication?
 - One
 - Two
 - 3 or more
 - Zero
- 7. On a scale of 1-5 (1 being the least helpful, and 5 being the most helpful), how helpful do you feel calls to patients improve asthma management?
 - 1
 - 2
 - 3
 - 4
 - 5
- 8. On a scale of 1-5 (1 being the least useful, and 5 being the most useful) how much do you think the parents found your call useful?
 - 1
 - 2
 - 3
 - 4
 - 5

Qualitative Questions:

1. What do you find useful about the Propeller dashboard?
2. What changes do you think are needed to improve the Propeller dashboard?
3. How are you currently using the Propeller dashboard? Please describe.
4. Would you utilize the Propeller health management platform for your current practice in the future?

Sample Size Determination:

Assuming asthma exacerbation rate of 0.545 for the intervention arm, and asthma exacerbation rate of 0.75 for the standard treatment arm, resulting odds ratio (OR) equal to 0.3992674, and $\log(\text{OR}) = -0.9181239$. Assuming 20% patient drop-out rate, two-sided significance level $\alpha = 0.05$, a total of 250 patients (125 per arm) is needed in order to achieve a statistical power of 85%. The sample size calculation was computed using SAS procedure PROC SEQDESIGN.

Qualitative Analyses of Semi-Structured Interviews:

Data will be analyzed systematically using a constant comparative approach; and four analysts (i.e., coders), including [name] (qualitative methods expert), [name], and 2 research team members, will meet to discuss initial thoughts, insights, and observations for the development of initial coding categories (e.g., themes). Through a systematic analysis process, themes will be continually refined by collapsing redundant themes and removing irrelevant themes. Once no new categories have emerged, a

codebook will be developed for the remaining analysis. We will construct a saturation grid, to track themes as they emerge and determine when no new information is obtained

Study Staff:

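### Four unranked primary outcomes, each with its own treatment-term model, and no stated rule for which result makes the trial positive

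*SAP*

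**What the plan says.** **Primary outcomes.** The Protocol's Data Analysis section, under Primary Outcomes, lists ACT, asthma-related hospitalizations, asthma-related ED visits and asthma-related oral corticosteroid use. They have equal status and no order.

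**Models.** AIM 1 of the SAP, repeated in the Protocol's Statistical Analysis section, gives each outcome its own model. For the three counts: "Each count variable (asthma-related oral corticosteroid use, ED visits, and hospitalizations) will be analyzed by mixed negative binomial regression analysis adjusting for treatment". For ACT: "For each continuous primary outcome variable (i.e., ACT score), change-from-baseline score at each visit will be analyzed using mixed linear regression models". The ACT model also has a treatment-by-time interaction, although the same section defines the ACT outcome as the change to 12 months. In both model types the final model is chosen for parsimony, using fit criteria, parameter estimates and their precision.

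**Purpose.** The Design item of Study Design and Procedures describes a comparison of arms: "We will conduct a randomized controlled trial comparing asthma inhaler use and asthma-related outcomes between children who either receive the Remote Health Management Platform". No other section tests the four primary outcomes by arm, so I read the treatment terms in AIM 1 as the efficacy tests. That is an inference; the plan does not say so.

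**Planning.** Sample Size Determination uses a single quantity at two-sided 0.05: "Assuming asthma exacerbation rate of 0.545 for the intervention arm, and asthma exacerbation rate of 0.75 for the standard treatment arm". The only other alpha, 0.05 for baseline comparisons, is described as descriptive.

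**Not found.** The available text has no hierarchy, alpha split, adjustment, co-primary rule or definition of a positive trial. A few pages were not available for review.

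**The concern.** With four primary outcomes and no decision rule, a significant result on any one could be reported as the primary finding, and nothing in the plan would contradict that. If each were tested at the planning level of 0.05, that reading would not hold the 5% error for which the trial was sized.

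A reader also cannot tell which result decides the trial or which one the 250 patients support. The planning quantity is a proportion expressed through an odds ratio, and none of the four outcomes is analysed as a proportion.

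For ACT, the plan models every visit and does not say which treatment contrast is the test. The data-driven choice of model leaves a further decision open until results are seen.

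**Working it through.** **1. Reproduce the plan's own figure.** Inputs from Sample Size Determination: proportions 0.545 and 0.75, log(OR) = -0.9181, two-sided 0.05, 85% power, 20% drop-out.

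- Variance term: V = 1/(0.545 × 0.455) + 1/(0.75 × 0.25) = 4.033 + 5.333 = 9.366.
- n per arm = (1.960 + 1.036)² × V / 0.9181² = 99.76, rounded up to 100.
- Drop-out: 100 / 0.8 = 125 per arm, 250 in total.

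This matches the Protocol. The calculation covers one test of one quantity at 0.05.

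**2. Familywise error if any one outcome counts.** The documents give neither this rule nor a correlation. Assumed: four two-sided tests at 0.05, each holding exactly 5%, jointly normal, with common pairwise correlation r.

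- Independent: 1 - 0.95⁴ = 1 - 0.8145 = 0.1855.
- Correlated: with c = 1.96, 1 - ∫ φ(u) [Φ((c - √r·u)/√(1-r)) - Φ((-c - √r·u)/√(1-r))]⁴ du.

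| r | Each at 0.05, any one counts | Holm, no outcome has an effect |
|---|---|---|
| 0 | 18.5% | 4.9% |
| 0.5 | 15.6% | 4.3% |
| 0.8 | 11.4% | 3.2% |
| 0.9 | 9.4% | 2.6% |
| 0.95 | 8.0% | 2.2% |
| 0.99 | 6.3% | 1.6% |

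Simulation with 2 million draws agreed at 0.5, 0.8 and 0.95. The Holm column uses its first step, 0.05/4 = 0.0125; for independent tests it is 1 - 0.9875⁴ = 0.0491. The unadjusted error falls to 5% only at perfect correlation.

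**3. Power cost of Holm on the planning effect.** At 100 evaluable per arm, |log(OR)| / √(V/100) = 0.9181 / 0.3060 = 3.000. Power = Φ(3.000 - z).

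| Alpha at the step | z | Power |
|---|---|---|
| 0.05 | 1.960 | 85.1% |
| 0.025 | 2.241 | 77.6% |
| 0.0167 | 2.394 | 72.8% |
| 0.0125 | 2.498 | 69.2% |

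To keep 85% at 0.0125: (2.498 + 1.036)² × 9.366 / 0.9181² = 138.8, so 139 evaluable or 139/0.8 = 174 enrolled per arm.

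**4. Power under an all-four rule.** Assuming each outcome alone had 85% power: 0.85⁴ = 52% if independent, about 64% at r = 0.5 and 77% at r = 0.9.

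**5. Does any section supply a ranking by implication?**

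- The sample size names an exacerbation rate, which is not a listed primary outcome. The baseline data list in Enrollment/Visit 1 separates exacerbation history from corticosteroid courses. In the other direction, the third inclusion criterion ties an exacerbation to a course of oral corticosteroids, and Study Subjects restates that requirement simply as having received them. The rate may therefore mean oral corticosteroid courses, but no section says so.
- The SAP attaches the word primary only to ACT, in a sentence limited to continuous outcomes. That is consistent with the three counts being the non-continuous primaries and does not put ACT first.

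**The case against.** The strongest reply is that no inflation has been shown. The error rates need an any-one rule, testing at 0.05 and an assumed correlation, and none of these is in the analysis text. This stands. A reader might infer that the trial runs an 18.5% false-positive risk. The documents do not support that, because they neither state nor exclude an any-one rule, and an all-four rule would bring no inflation. What the documents do show is that the decision rule is absent.

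A reader might also infer that the trial was sized on something unrelated to its primary outcomes. That goes too far: the eligibility wording suggests the exacerbation rate may be the corticosteroid outcome. It still creates no hierarchy.

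A third point also stands: a multiplicity rule alone does not secure 5%. Holm needs valid individual tests, and choosing each model by its fit or estimates undermines that. The fix has to cover model choice as well.

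Finally, leaving the baseline count out of the count models is not an error. A randomized comparison is valid without it, so adding it is an efficiency gain and separate from the main point.

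**Conclusion.** The concern holds as a missing decision rule. Four primary outcomes have equal status, each has its own treatment term, and the available text does not say how their results combine.

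The size is conditional. If any one result at two-sided 0.05 counted as success, familywise error would be 18.5% under independence, 11.4% at correlation 0.8 and 8.0% at 0.95, assuming one exact 5% test per outcome and equal correlations. Selecting among ACT contrasts or models after seeing results could add to this. Correlation between the outcomes does not remove the problem short of perfect correlation.

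The rule must be settled before outcomes are analysed by arm. Confidence is high on the text and the arithmetic; which rule the sponsor intended is unknown.

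**What to change.** Before outcomes are analysed by arm, amend the Protocol (Primary Outcomes, and AIM 1 of Statistical Analysis) and AIM 1 of the SAP:

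1. **Decision rule.** Test the four treatment effects with Holm at familywise two-sided 0.05: ordered p-values against 0.0125, 0.0167, 0.025 and 0.05, stopping at the first failure. Alternatively, the sponsor names one primary outcome, a fixed testing order at 0.05 each that stops at the first non-significant result, or an all-four rule. Which outcome leads is the sponsor's choice.
2. **Planning quantity.** Define the exacerbation rate in Sample Size Determination and link it to a listed primary outcome.
3. **ACT test.** State that it is the treatment contrast at 12 months, which matches the SAP's outcome definition.
4. **Model.** For these tests, fix the model in advance as treatment plus the covariates already listed (with time point, its interaction with treatment, and baseline score for ACT). Do not choose it by fit criteria or parameter estimates; otherwise no rule secures 5%.
5. **Separate improvement.** Add the prior-year count to each count model, from the previous-year EMR data the Protocol already collects (Enrollment/Visit 1; Timeline, Phase 1). Eligibility requires at least one prior-year oral corticosteroid course, so that covariate starts at 1.

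**Cost.** These are wording changes and need no new data. With Holm, power on the planning odds ratio at 100 evaluable per arm falls from 85% to 69% at the strictest step. Restoring 85% there would take about 139 evaluable per arm; I would restate the power and not enrol more. With one named primary, three outcomes lose primary status. An all-four rule costs the joint power shown above. No power is given for the planned negative binomial or ACT models, so 85% should not be claimed for them.

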# Missing data and sensitivity analyses:

Missing data will be handled using Multiple Imputations. Sensitivity analyses will be conducted using SAS procedures PROC MI and PROC MIANALYZE. Other sensitivity analyses may be performed if appropriate.

AIM 2. Enhance parental management through improved inhaler use.

After the patient's enrollment visit, parents will be contacted via email or phone at 1, 3, 6, 9, and 12 months to complete a REDCap survey. Descriptive statistics (frequencies and percentages) of each quantitative question will be summarized at each time point and associations between outcomes and demographic predictors will be analyzed by Chi-squared test. Qualitative data will be coded and analyzed by theme analysis.

AIM 3. Improve management by physician and clinical team.

On a biweekly basis, we will collect quantitative data from clinics on the number of time physicians' follow-up with patients and the follow-up outcome. The research team will know exactly how many alerts physicians are receiving, and how physicians are following-up with patients from the Propeller dashboard. The data from the Propeller dashboard will be summarized and associations between outcomes and clinic predictors will be analyzed by Chi-squared test. Clinicians will also be contacted at 1, 3, 6, 9, and 12 months through REDCap surveys to determine if the data is helping them with management and aspects of the platform they like and dislike. Descriptive statistics (frequencies and percentages) from surveys will be summarized at each time point and associations between outcomes and clinic predictors will be analyzed by Chi-squared test.

Qualitative data will be coded and analyzed by theme analysis.

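### The count models for the three 12-month-rate primary outcomes name no follow-up-time offset, and the plan does not say how part-year counts are handled

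*SAP*

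**What the plan says.** The SAP (AIM 1) lists among the outcomes of interest "the 12-month rate of asthma-related oral corticosteroid use, ED visits, and hospitalizations". With the ACT score, these are the protocol's primary outcomes (Data Analysis, Primary Outcomes). Each count "will be analyzed by mixed negative binomial regression analysis adjusting for treatment, all potential predictors" and random effects of family and clinic. The protocol's own AIM 1 text is the same. Neither document mentions an offset, exposure or person-time. The paragraph on ACT includes a time-point term and the count paragraph does not, so the natural reading is one total per child.

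The sample size section of the protocol plans for incomplete follow-up: "Assuming 20% patient drop-out rate". It gives one overall figure, with no split by arm and no timing.

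On missing data the SAP says "Missing data will be handled using Multiple Imputations". It does not say whether event counts are imputed, at what level (interval or yearly total), or how a child with part of a year is classed.

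Events come from two sources: a monthly pull from the electronic medical record (EMR), and parent report in the follow-up surveys. The protocol gives the reason for the second source in its survey items (Study Design and Procedures, items 8 to 12): the EMR can miss visits made outside the network.

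**The concern.** A yearly rate needs a denominator. If a child is observed for four months and the count goes into a model with no exposure term, those four months are treated as twelve. The estimated rate is then too low. If one arm loses more follow-up than the other, that arm also appears to have fewer events, and the treatment comparison is distorted.

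Unequal loss is plausible here: the trial is not double-blind (item 6) and only the intervention arm has the sensor and app (item 7). Observation time may also vary among completers, because the final visit is meant to be aligned with the child's annual clinic visit (item 12).

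Two analysts could both follow the plan and obtain different results on three primary outcomes.

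**Working it through.** **1. The plan's own figure.** The protocol states that "a total of 250 patients (125 per arm) is needed in order to achieve a statistical power of 85" per cent. Its inputs are 0.545 and 0.75, two-sided alpha 0.05 and 20% drop-out.

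- OR = (0.545/0.455)/(0.75/0.25) = 0.3993; log OR = -0.9181. Both match the protocol.
- n per arm = (1.960 + 1.036)² × [1/(0.545 × 0.455) + 1/(0.75 × 0.25)] / 0.9181² = 99.76, so 100.
- 100/(1 - 0.20) = 125 per arm, 250 in total, as stated.

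This is a binary calculation that contains no follow-up time, so an offset does not alter it. The 20% acts only as an inflation factor.

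**2. Mean observed exposure.** Let d be the drop-out proportion, f the average fraction of the year observed before drop-out, and c the fraction of later events still captured. Effective exposure is 1 - d(1 - f)(1 - c). Without an offset, the expected rate ratio is the true ratio times (intervention exposure / control exposure).

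Assumptions not in the documents: the arm splits below, f = 0.5 (drop-out uniform over the year) and c = 0. With no true effect:

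| Drop-out, intervention / control | Exposure, intervention | Exposure, control | Apparent rate ratio |
|---|---|---|---|
| 20% / 20% | 0.90 | 0.90 | 1.000 |
| 25% / 15% | 0.875 | 0.925 | 0.946 |
| 30% / 10% | 0.85 | 0.95 | 0.895 |
| 10% / 30% | 0.95 | 0.85 | 1.118 |

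At 20% in both arms each rate is understated by 10% and the ratio is unchanged.

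**3. Sensitivity to the assumptions.** For 30% / 10%, f from 0.25 to 0.75 gives 0.775/0.925 = 0.838 to 0.925/0.975 = 0.949. For 10% / 30% the range is 1.194 to 1.054. If f = 0.5 and the EMR captures half of the later events (c = 0.5), 30% / 10% gives (1 - 0.3 × 0.25)/(1 - 0.1 × 0.25) = 0.925/0.975 = 0.949, about half the distortion.

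**4. With the planned effect.** Read 0.545 and 0.75 as yearly rates (an assumption, since the protocol uses them as proportions). The true ratio is 0.727. With f = 0.5 and c = 0:

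- 30% / 10%: (0.545 × 0.85)/(0.75 × 0.95) = 0.650.
- 10% / 30%: (0.545 × 0.95)/(0.75 × 0.85) = 0.812.

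**5. Simulation.** Negative binomial counts, 125 per arm, 600 replicates, dispersion 0.5 and 1.0. Treatment was the only covariate, there were no random effects, dispersion was taken as known, and drop-out was unrelated to event risk. With no true effect and 30% / 10% drop-out, two-sided type I error was 10.3% and 8.7% without an offset, and 4.3% and 5.5% with one. The Monte Carlo standard error at 5% is √(0.05 × 0.95/600) = 0.9 percentage points. With the planned effect, the offset model's average ratio was 0.71 to 0.74 in every drop-out pattern.

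**6. The other route.** Suppose part-year children are set missing. At 20% drop-out and f = 0.5, the events discarded are (0.20 × 0.5)/0.90 = 11% of those observed. In the same simulation, analysing complete children alone gave average ratios of 0.71 to 0.74, so the cost there was precision, not bias.

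**The case against.** A reader might infer that the plan must either count part of a year as a full year or throw observed events away. The documents do not support that. The SAP does not rule out an offset. It names multiple imputation, and imputation by interval would keep the observed events and fill in only the unobserved months.

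A reader might also equate drop-out with loss of event data. The EMR is pulled monthly whether or not surveys are returned, and enrolment is limited to children cared for at study clinics. A family that stops answering at month 4 may still have twelve months of in-network events. What is lost for certain is parent-reported, out-of-network events. The documents do not say whether pulls continue after withdrawal.

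Finally, the only documented drop-out figure is a single 20%, and equal drop-out does not bias the rate ratio. Nothing in the documents shows that the treatment comparison will be biased.

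All of this stands and limits the size of the problem. It does not remove it. The imputation sentence is too short to settle the handling of part-year counts, EMR capture is incomplete by the protocol's own account, and the model as written has no term for unequal observation. The objection also bears on the remedy: two sources with different observation windows cannot be reconciled by one undefined exposure variable.

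**Conclusion.** The point holds as a gap in the model specification. The outcome is a 12-month rate, drop-out is expected, and neither the count model nor the imputation sentence says how a part-year count is handled. The consequence depends on what is done:

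- **Part-year counts entered as they are:** absolute rates are understated by about 10% at 20% drop-out, given uniform timing and no later capture. The rate ratio is untouched if drop-out is equal. At an assumed 30% versus 10% it is 0.895 with no true effect, with type I error of about 9 to 10%. The bias in the ratio is about halved if the EMR captures half of the later events.
- **Yearly totals imputed:** observed events are discarded, which mainly costs precision when drop-out is unrelated to event risk.
- **Imputation by interval:** neither problem arises from the handling of observed events.

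The arm splits, the timing and the degree of EMR capture are illustrations, not figures from the documents. The plan should be corrected before analysis, but it does not show that a biased result is inevitable.

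**What to change.** In the SAP (AIM 1) and the matching protocol text:

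1. Add log(observed follow-up time) as an offset in each of the three count models.
2. Continue EMR ascertainment to month 12 for children whose caregivers stop answering surveys, unless consent is withdrawn.
3. Define the end of exposure separately for EMR events and parent-reported events. One way to deal with the two windows is a sensitivity analysis of EMR events only, over the EMR window.
4. State that any imputation of counts is done by interval and keeps observed events.

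The offset corrects for unequal observation time, assuming a constant rate over the year and drop-out unrelated to event risk given the covariates. It does not recover out-of-network events after surveys stop, which is why item 3 is needed.

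The cost is one or two derived variables and a little more analysis. The stated sample size of 250 is unchanged.
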